### **3.1 Inclusion Criteria**

Male adolescents who meet the following criteria are eligible for inclusion in this study:

- 3.1.1** Assigned male at birth (includes MSM, TGW, and gender non-conforming people)
- 3.1.2** At enrollment, aged below 18 years\*
- 3.1.3** At enrollment, body weight  $\geq 35$  kg (77 lbs.)\*
- 3.1.4** Willing to provide written informed assent/consent for the study and/or able to obtain written parental/guardian informed consent;
- *If not of legal age or otherwise not able to provide independent informed consent as determined by local law and consistent with site IRB/EC policies and procedures: Parent or legal guardian is willing and able to provide written informed consent for study participation and potential participant is willing and able to provide written assent for study participation.*
- *If of legal age or otherwise able to provide independent informed consent as determined by local law and consistent with site IRB/EC policies and procedures: Willing and able to provide written informed consent for study participation.*
- 3.1.5** Self-reported sexual activity with a male in the past 12 months;
- 3.1.6** In general, good health, as evidenced by the following laboratory values:
  - Non-reactive / negative HIV test results\*\*,
  - Absolute neutrophil count  $> 799$  cells/mm^3,  $\pm$
  - Platelet count  $\geq 100,000$  cells/mm^3,
  - Hemoglobin  $\geq 11$ g/dL,  $\pm$
  - Calculated creatinine clearance  $\geq 60$  mL/minute using modified Schwartz equation ( $\leq$  grade 2),
  - Alanine aminotransferase (ALT)  $< 2.0$  times the upper limit of normal (ULN) and total bilirubin (Tbili)  $\leq 2.5 \times$  ULN,
  - Hepatitis B virus (HBV) surface antigen (HBsAg) negative and accepts vaccination,
  - HCV Antibody negative.

**3.1.7** Willing to undergo all required study procedures

**3.1.8** If currently on PrEP from a non-study source, willing to stop said PrEP prior to enrollment and agree to switch to oral CAB for the lead-in period and CAB LA injections.

\*Please see [Section 1.7](#) for explanation.

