2. INTRODUCTION

This SAP is intended to describe the final primary and secondary analyses upon completion of HPTN083-01. Sections of the SCHARP SAP template had to be adapted here to reflect the distinct single-arm outcomes, as opposed to the more common multi-arm studies that the template was designed for. Key variable definitions are included in Appendix B.

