2.1 General Design Considerations

HPTN083-01 is a phase IIB single arm trial designed to establish the minimum safety, tolerability and acceptability data needed to support the use of cabotegravir long-acting injection (CAB LA) in an adolescent population, potentially transforming the field of HIV prevention for young people. The study target population is sexually active, healthy male adolescents aged below 18 years. The study target is to enroll more than 50 participants with at least 50 participants receiving at least one injection. Participant recruitment will take approximately 12 months.

Study participation includes Step 1: a 5-week oral CAB 30mg QD safety lead-in followed by Step 2: a series of 5 intramuscular (IM) injections of 3 mL (600 mg) cabotegravir administered at 8-week intervals after a 4-week loading dose (injections at weeks 5, 9, 17, 25 & 33). Adherence support strategies (e.g., counseling, reminders, pill cases) will be included to support pill-taking during the first five weeks and to support retention during the injectable phase. A safety visit will follow each injection to ascertain pharmacokinetic-peak safety data, including injection site reactions. Step 3: A blood draw visit, the +8 Week Visit, will follow the week 33 injection to monitor CAB drug levels. All participants who have received at least one injection will be followed for 48 weeks after their last injection. Waning levels of cabotegravir (the PK tail) will be covered with locally sourced oral TENOFOVIR/EMTRICITABINE (TRADE NAME: TDF/FTC, TRUVADA®) for daily use for 48 weeks. In Step 3 participants may also choose to continue with 8-week dosing of injectable of CAB-LA for 48 weeks (5 additional injections beyond the initial 5 injections, administered at weeks +8, +16, 24, +32, +40, and +48.) Behavioral and acceptability data will be collected via computer-assisted self-interview (CASI). Total participant commitment for the entire study is up to 87 weeks, or approximately 1.5 years. We anticipate recruitment for the study will take approximately 12 months.

Participants who discontinue study product during Step 2 for any reason other than HIV infection or AE occurrence will be transitioned to open label TDF-FTC for 48 weeks.

There are in total three study sites:

- Adolescent and Young Adult Research at the Core Center (AYAR at CORE), Chicago, IL;
- St. Jude Children's Research Hospital CRS, Memphis, TN;
- Fenway Health CRS, Boston, MA.

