6. TRIAL PARTICIPANT DISPOSITION

6.1 Disposition of Participants

The study will recruit participants to ensure that at least 50 participants progress to the injection phase, therefore more than 50 participants will be screened and enrolled.

Consort Diagram

¹Conditions in Step 1 that could disqualify a participant from transitioning to Step 2 are as follows:

- Pill count suggestive of less than 50% adherence at the Week 4 visit
- Missed or delayed Week 4 visit
- Grade 2 ALT at week 4, or grade 3 and above ALT anytime in step 1
- Grade 3 AE that is related to study product anytime in step 1, excluding ALT & CPK
- Grade 4 AE anytime in step 1, excluding ALT & CPK
- Grade 3 and above CPK and < Grade 3 ALT
- At substantial risk of HIV infection and/or qualifies for oral PrEP by local guidelines
- Any HIV reactive/positive test

Participant enrollment inclusion and exclusion criteria (see study protocol)

A. Inclusion Criteria

- 1) Assigned male at birth (including MSM, TGW, and gender non-conforming people)
- 2) At enrollment, below 18 years of age
- 3) At enrollment, body weight ≥ 35 kg (77 lbs.)
- 4) Willing to provide written informed assent/consent for the study and/or able to obtain written parental/guardian informed consent
- 5) Self-reported sexual activity with a male in the past 12 months
- 6) In general, good health, as evidenced by the following laboratory values:
 - a. Non-reactive / negative HIV test results
 - b. Absolute neutrophil count > 799 cells/mm³
 - c. Platelet count $\geq 100,000$ /mm³
 - d. Hemoglobin > 11 g/dL
 - e. Calculated creatinine clearance ≥ 60 mL/minute using the modified Schwartz equation (\leq grade 2)
 - f. Alanine aminotransferase (ALT) < 2.0 times the upper limit of normal (ULN) and total bilirubin (Tbili) $\leq 2.5 \times$ ULN
 - g. Hepatitis B virus (HBV) surface antigen (HBsAg) negative and accepts vaccination
 - h. HCV Antibody negative
- 7) Willing to undergo all required study procedures
- 8) If currently on PrEP from a non-study source, willing to stop said PrEP prior to enrollment and agree to switch to oral CAB for the lead-in period and CAB LA injections.

B. Exclusion Criteria

- 1) Co-enrollment in any other HIV interventional research study or other concurrent studies which may interfere with this study (as provided by self-report or other available documentation);
- 2) Past or current participation in HIV vaccine trial with exception for participants who can provide documentation of receipt of placebo;

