6.4 Unplanned enrollment discontinuation

In January 2022 the HPTN leadership determined that the study accrual rate was insufficient to meet the target enrollment in a reasonable amount of time, and study enrollments were stopped after a total accrual of nine participants.

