7. BASELINE DATA

The following data will be described overall, and by site:

Demographics (Table 1):

- Age (continuous – mean, SD, median, min max; categorical (≤ 16 , > 16): n (%))
- Gender identity
- Race
- BMI
 - Age standardized BMI z-score (continuous – mean, SD, median, min max)
 - Classification as obese, overweight, normal, thinness, severe thinness based on z-score
 - *Note: The Clinical Study Report will report BMI without the use of z-scores*
- Housing security*
 - Do you have a regular place or home where you stay and store your things? (yes/no)
- Food security*
 - In the past 6 months, how frequently did you worry that your household would not have enough food?

Sexual behaviors / HIV Risk Perception (Table 2):

During the past month the participant had*:

- a primary partner
- transactional sex with male sex partners
- # male and/or transgender female sex partners
- # male and/or transgender female sex partners who are reported to be HIV positive
- # episodes of receptive anal sex
- # episodes of receptive anal sex without condom
- # episodes of receptive anal sex without condom, with HIV+ or unknown partner
- # episodes of insertive anal sex
- # episodes of insertive anal sex without condom
- # episodes of insertive anal sex without condom, with HIV+ or unknown partner
- STIs present at enrollment:
 - Gonorrhea
 - Trachomatis
 - Syphilis
- Hepatitis testing at screening/enrollment
 - HBV
 - HCV

- HIV risk perception*:
 - How much do you personally feel at risk of getting infected with HIV?

Mental health (Table 3):

- Depression indices¹
 - CES-D-10* (continuous – mean, SD, median, min max; categorical (≤ 10 : not depressed, > 10 : depressed): n (%))
 - PHQ9 (continuous – mean, SD, median, min max; categorical (none-minimal, mild, moderate, moderately severe, severe): n (%))
- Intimate partner violence (IPV)*
 - In the past 6 months, have any of your partners punched, slapped, kicked, bit you, or caused you any type of physical harm?
 - In the past 6 months, have any of your partners insulted, ignored or humiliated you, yelled at you, or made you feel ashamed or bad about yourself?
 - In the past 6 months, have any of your partners forced you to have sex or perform any sexual act, or touched you sexually in any way that you did not want?
 - In the past 6 months, have any of your partners made you feel afraid, unsafe or in danger?

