(2) https://cdn.who.int/media/docs/default-source/child-growth/growth-reference-5-19-years/computation.pdf?sfvrsn=c2ff6a95_4

Age-specific values of necessary parameters $L(t)$, $M(t)$, and $S(t)$ can be downloaded from the website (1) (see section: “**Expanded tables for constructing national health cards**” link to dataset “**z-scores: girls**”)

Categorical BMI classification based on age-standardized BMI z-score as follows:

- Obesity: $>+2$
- Overweight: $>+1$ and $\leq+2$
- Normal: >-2 and $\leq+1$
- Thinness: >-3 and ≤-2
- Severe thinness: ≤-3

16. APPENDIX C – Imputation of missing dates

Missing Start and Stop Dates for Prior and Concomitant Medication, and Medical History

The Assumption is to consider the most conservative judgment when imputing.

Start date:

When imputing a start date ensure that the new imputed date is sensible i.e. is prior to the end date and the general rules are:

1. If start date is completely missing, start date will not be imputed
2. If year and month are present and day is missing, set day to the 1st day of month.
3. If year and day are present and month is missing, then set month to January.
4. If year is present and month and day are missing, set month and day to January 1st.

Stop date:

1. If end date is completely missing, end date will not be imputed
2. If year and month are present and day is missing, set day to the last day of month.
3. If year and day are present and month is missing, set month to December
4. If year is present and month and day are missing, set month and day to December 31st.

Missing Start and Stop Dates for Adverse Events (including ISRs)

The Assumption is to consider the most conservative judgment when imputing.

Start date:

1. If start date is completely missing, start date is set to date of first dose.
2. If (year is present, and month and day are missing) or (year and day are present, and month is missing):
 - a. If year = year of first dose, then set month and day to month and day of first dose.
 - b. If year < year of first dose, then set month and day to December 31st.
 - c. If year > year of first dose, then set month and day to January 1st.
3. If month and year are present and day is missing:
 - a. If year = year of first dose and
 - i. If month = month of first dose, then set day to day of first dose date.
 - ii. If month < month of first dose, then set day to last day of month.
 - iii. If month > month of first dose, then set day to 1st day of month.

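### The SAP takes BMI z-score parameters from the girls' reference for a cohort assigned male at birth, and gives two conflicting CES-D-10 cut-offs

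*SAP*

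**What the plan says.** **BMI z-score.** SAP Section 2 says where definitions are kept: "Key variable definitions are included in Appendix B". Item 4 of that appendix bases the z-score on the WHO growth reference for ages 5 to 19. For the age-specific parameters L(t), M(t) and S(t) it names one dataset, "z-scores: girls". No boys' dataset is named in either document. The z-score is used in SAP Section 7, Table 1, as a continuous summary and as a five-level category: "Classification as obese, overweight, normal, thinness, severe thinness based on z-score". Section 7 also states that the Clinical Study Report (CSR) will present BMI without z-scores.

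**Who is in the trial.** Protocol Section 3.1 admits only people who meet this criterion: "Assigned male at birth (includes MSM, TGW, and gender non-conforming people". SAP Section 6.1 repeats it: "Assigned male at birth (including MSM, TGW, and gender non-conforming people".

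**CES-D-10.** SAP Section 7, Table 3, splits the score so that totals up to and including 10 are not depressed and totals above 10 are depressed. Appendix B, item 1, sums ten items scored 0 to 3 and treats any total of 10 or more as depressed.

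**Size and layout.** SAP Section 6.4 records that "study enrollments were stopped after a total accrual of nine participants". SAP Section 2.1 states: "There are in total three study sites". Section 7 opens with: "The following data will be described overall, and by site".

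**The concern.** A BMI-for-age z-score places a person relative to a reference population of the same age and sex. The WHO reference is supplied by sex, and the SAP points to the table for the sex that no participant was assigned at birth. An analyst who follows Appendix B literally will compute every z-score from the wrong L, M and S. The continuous summary will be wrong throughout, and anyone near a class boundary (-3, -2, +1 or +2) may be put in the wrong BMI class.

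The CES-D-10 problem is of a different kind. Two current sections of the same SAP give opposite labels to the same score, so the reported proportion depressed depends on which section the programmer reads. The category also feeds the addendum to Table 3: the cross-tabulation of CES-D-10 against PHQ-9, and the scatterplot coloured by whether the two indices agree.

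At stake is the accuracy of the baseline description of a very small cohort. No endpoint inference is affected.

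**Working it through.** **1. Reference sex for the BMI z-score**

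| Place | What it fixes |
|---|---|
| SAP Appendix B, item 4 | Parameters come from the girls' dataset; no alternative given |
| Protocol Section 3.1; SAP Section 6.1 | All participants assigned male at birth |
| SAP Section 7, Table 1 | z-score summarised as a continuous variable and in five classes |
| SAP Section 7, note to Table 1 | CSR reports BMI without z-scores |

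Each z-score is a function of the participant's BMI and of L, M and S at that age. If L, M and S come from the wrong table, all z-scores are affected: 9 of 9 if every participant has a BMI and an age. Raw BMI does not use these parameters and is unaffected.

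The size of the shift cannot be derived. The documents contain no L, M or S values and no participant BMI data, so neither the average shift nor the number of changed classes can be stated.

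**2. CES-D-10 cut-off**

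Inputs: ten items, each 0 to 3 (Appendix B, item 1), so totals run from 0 to 30, which is 31 values.

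| Total | Section 7 | Appendix B |
|---|---|---|
| 0 to 9 | not depressed | not depressed |
| 10 | not depressed | depressed |
| 11 to 30 | depressed | depressed |

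Applying both rules to every attainable total gives disagreement at 10 only: 1 of 31 values. This counts score values; it is not the probability that a participant is affected.

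*Is it only notation?* PC-PTSD-4 serves as a control. Its totals run from 0 to 4. Section 7 flags totals above 2 and Appendix B flags totals of 3 or more. For whole numbers these are the same rule, with disagreement at 0 of 5 totals. The two sections are therefore consistent for one instrument and inconsistent for the other.

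**3. Effect of one participant scoring exactly 10**

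Shift in the proportion depressed = 1/n, where n is the number with a score.

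- Overall, nine scored: 1/9 = 11.1 percentage points.
- At the planned 50, for comparison: 1/50 = 2.0 points.
- By site: site sizes are not given. Assuming each of the three sites enrolled at least one of the nine, a site has between 1 and 9 - 2 = 7 participants. The shift is then between 100/7 = 14.3 and 100/1 = 100 points, and 100/3 = 33.3 points at an even split. Without that assumption a single site could hold all nine, and the lower end falls to 11.1 points.

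**4. Reach**

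| Output | BMI z-score error | CES-D-10 conflict |
|---|---|---|
| Primary and secondary endpoints | none | none |
| Baseline tables outside the CSR | Table 1 | Table 3 and its addendum |
| CSR | excluded by Section 7 | addendum excluded; no exclusion stated for the CES-D-10 categories |

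**The case against.** The textual facts are hard to dispute, so the case on the other side is about weight.

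- **The effect is descriptive and partly outside the CSR.** This stands. Neither variable enters an endpoint, and the z-score cannot reach the CSR.
- **The BMI consequence is unquantified, and the SAP only says where the values can be obtained.** The first part stands: confidence attaches to the wrong dataset label, not to any particular change in results. The second does not remove the problem, because this is the only source given.
- **Transgender women are eligible, so a girls' reference might be deliberate.** The criterion also covers MSM and gender non-conforming people, and the SAP states no rule by gender identity. A girls-only table for everyone is not explained this way. Carry-over is a more likely source: the SAP change history says most version 2.0 revisions were made to harmonize with the HPTN 084-01 SAP, and the protocol describes HPTN 084 as a trial in women. That is inference only.
- **The by-site figures mostly reflect tiny denominators, and nobody is known to have scored 10.** Both points stand. The site range rests on an assumption. Section 7 also names no analysis population for the baseline tables, and Appendix B sets the CES-D-10 score to missing if any item is missing, so n could be below nine.
- **Section 2 does not say that Appendix B overrides Section 7.** This also stands. It says where key definitions are kept and gives no order of precedence. Which cut-off was intended cannot be settled from the documents.

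**Conclusion.** Both defects are present in the current SAP text, and nothing elsewhere in either document resolves them.

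The BMI instruction is wrong as written for this population. It affects every computed z-score in Table 1, by an amount the documents do not allow one to calculate. Whether any BMI class changes is unknown.

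The CES-D-10 text cannot be followed consistently. The conflict is confined to a total of 10, but each participant with that score moves the overall proportion depressed by 11 points, assuming all nine have a score. The effect within a site is at least as large. It is also the part that may reach the CSR.

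These errors should be corrected, but they do not threaten the trial's conclusions: the damage is limited to baseline description.

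**What to change.** 1. In Appendix B, item 4, replace the girls' dataset with the WHO boys' dataset. Alternatively, state and justify one reference-sex rule that explicitly covers transgender women and gender non-conforming participants.
2. State one CES-D-10 cut-off in both Section 7 and Appendix B, item 1. Appendix B is a reasonable starting point because Section 2 directs the reader there for definitions, but the sponsor needs to confirm which cut-off was intended.
3. Produce the z-score and BMI-class rows of Table 1, the CES-D-10 rows of Table 3, and the CES-D-10/PHQ-9 addendum under the corrected rules. If they have already been run, regenerate them.

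The cost is two wording corrections and a rerun of parts of two baseline tables and one addendum. No new data are needed.

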## **5.2 Enrollment**

### **Baseline/Enrollment/Week 0 Visit**

Both clinical and laboratory evaluations will occur at this visit, along with behavioral and acceptability assessments, including administration of the Patient Health Questionnaire-9 (PHQ-9). See [Appendix I Schedule of Evaluations for Oral Phase – Step 1](#) for details.

All HIV test results including testing for acute HIV from Screening, which must be performed within 14 days of Enrollment, and at least one HIV test result from Enrollment must be available and confirmed to be negative/non-reactive PRIOR to provision of study product. Results from the chemistry testing, liver function tests (LFTs), lipid profile, hematology testing, and urinalysis from this visit are NOT required prior to enrollment.

Eligible participants will be reminded that the use of anticoagulant and/or antiplatelet medications as outlined in the SSP Manual are prohibited within seven days before and seven days after injections. Reminders will be built in to the concomitant medication history.

Participants will meet with study staff to receive education and information about adherence during the oral phase, identify potential barriers to adherence for the participant, and decide on adherence support strategies that will facilitate adherence. During counseling, participants will be offered supportive tools such as discrete pill containers, mobile reminder tools including text messaging and/or mobile app alerts, and weekly telephone check-ins from study teams.

All behavioral assessment measures will be programmed into CASI, with the exception of the PHQ-9, which is an eCRF administered only at Enrollment. Measures have been previously used either in adolescent biomedical prevention trials or in the Phase III adult trials of cabotegravir (HPTN 083/084).

At the end of this visit, participants will be dispensed oral cabotegravir, with first dose directly observed by study staff. Study product must be dispensed with instruction to participants.

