8.1 Safety endpoint analysis

Cohort: Injection population

Analysis description: Number and percent of participants experiencing any Grade 2 or higher clinical adverse events (AEs) or laboratory abnormalities (reported as adverse events) from the first injection visit to 8 weeks after the last Step 2 injection visit, or Week 41, whichever comes first. See Section 3.2 for details regarding aggregation and tabulation of AEs.

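### SAP Appendix C dates an undated AE or ISR to an undefined first dose; on the natural oral reading, undated injection-phase events leave the primary safety window

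*SAP*

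**What the plan says.** Appendix C has one set of rules under the heading "Missing Start and Stop Dates for Adverse Events (including ISRs"). Its stated principle is: "The Assumption is to consider the most conservative judgment when imputing". For start dates:

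- Fully missing: "If start date is completely missing, start date is set to date of first dose".
- Year known, month missing: "If year = year of first dose, then set month and day to month and day of first dose". A later year goes to 1 January.
- Day missing, in the year of first dose: "If month = month of first dose, then set day to day of first dose date". A later month goes to its first day.

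The SAP does not define the dose. Its variable definitions (Appendix B) cover only CES-D-10, PHQ-9, PC-PTSD-4 and BMI z-score. In Protocol 5.2, at the Week 0 visit, "participants will be dispensed oral cabotegravir, with first dose directly observed by study staff".

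The rules reach the primary safety endpoint by cross-reference. SAP 8.1 counts Grade 2+ events "from the first injection visit to 8 weeks after the last Step 2 injection visit" or Week 41, whichever is earlier, and adds: "See Section 3.2 for details regarding aggregation and tabulation of AEs". Section 3.2 refers missing dates to Appendix C, with no exception by phase or event type.

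The secondary safety windows are 12.2 item 1 (enrollment to Week 5), 12.2 item 2 (enrollment to 8 weeks after the last injection) and 12.3 (first injection visit to about 36 weeks later).

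**The concern.** Two safety windows open at enrollment and two open at the first injection, but there is one anchor. Dating an undated event to the start of treatment is cautious for a window that opens on that day, because the event is then counted. For a window that opens five weeks later it does the opposite: the event is placed before the window and disappears from it. That runs against the stated principle for 8.1 and 12.3. For ISRs the imputed date is impossible, because it precedes every injection.

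The primary safety proportion rests on very few people, since SAP 6.4 reports that enrollment stopped at nine. The AESI listings in Appendix A, which give time of onset and duration and include ISRs, would carry the same wrong dates.

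**Working it through.** The plan states no figure to reproduce. The check applies the Appendix C rules to the visit schedule.

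**Inputs.** Week 0 is day 0 (first oral dose, Protocol 5.2). Injections are at Weeks 5, 9, 17, 25 and 33 (SAP 2.1), which are days 35, 63, 119, 175 and 231. For a full course the 8.1 window closes at Week 41, day 7 × 41 = 287. At most nine were injected (SAP 6.4); the actual number is not given. Events are assumed to be assigned by onset date.

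**1. Fully missing date, oral anchor.** The imputed onset is day 0 whatever the truth.

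| Window | Days | Is day 0 inside? |
|---|---|---|
| 8.1 (primary) | 35 to 287 | no |
| 12.3 | 35 to about 287 | no |
| 12.2 item 1 | 0 to 35 | yes |
| 12.2 item 2 | 0 to 287 | yes |

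So 100% of fully undated injection-phase events leave 8.1 and 12.3 and enter the oral-phase count. None is lost from the aggregate window.

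**2. Undated ISR, oral anchor.** The gap to its own injection is 7 × (5, 9, 17, 25, 33) = 35, 63, 119, 175 or 231 days.

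**3. Partial date, oral anchor.** The documents give no enrollment dates, so each of the 365 Week 0 dates in 2021 was tried, with true onset on each of the 252 days from day 35 to day 286. The share misplaced into the oral phase is:

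- Year only: 0% to 100%. With Week 0 on 1 January, every injection-phase onset falls in the same year and is set to 1 January. With Week 0 on 27 November, the first injection is on 1 January, and so is every imputed date.
- Day missing: 0% to 30/252 = 11.9%. With Week 0 on 28 November, the first injection is on 2 January, and the 30 onsets from 2 to 31 January are all set to 1 January. With Week 0 on 25 January, the first injection is on 1 March and none is misplaced.

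For example, with Week 0 on 10 March and the first injection on 14 April, an event recorded only as April is dated 1 April, before the injection.

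**4. Injection as anchor instead.** Every fully undated oral-phase event of an injected participant moves to day 35, inside 8.1. Of oral-phase events, 0% to 100% (year only) and 0% to 30/35 = 85.7% (day missing) move in, again depending on the start date. Participants who began Step 1 but were never injected are in the Safety population and would have no anchor. So choosing an anchor does not by itself solve the problem.

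**5. Effect of one participant.** If the misplaced event is a participant's only Grade 2+ event in the window, the proportion moves by 1/n: 1/9 = 11.1 points, 1/8 = 12.5, 1/7 = 14.3. At n = 9, 1/9 has an exact (Clopper-Pearson) 95% CI of 0.3% to 48.2%; 0/9 has 0% to 1 − 0.025^(1/9) = 33.6%.

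**6. Two baseline definitions, side by side.** Appendix B takes the BMI z-score parameters from the WHO table for girls, while Protocol 3.1.1 requires assignment as male at birth. A CES-D-10 score of exactly 10 is classed as not depressed in SAP 7 and as depressed in Appendix B.

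**The case against.** **The term is less ambiguous than it looks.** The SAP speaks of the first or initial injection when it means that, and the protocol's first dose is oral. This stands. A reader might infer that two programmers would readily produce different counts; the documents give little support for the injection reading. But the oral reading is the one that empties 8.1 of undated injection-phase events, so settling the term that way does not remove the problem.

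**Assignment by onset date is an assumption.** The SAP windows are worded by visit. If events were assigned by the visit at which they were reported, an imputed onset would move nothing. This also stands as a condition. Onset is the better-supported reading: Protocol 7.7.1 counts events by when they occur, and 7.7.3 asks for events emerging during injectable dosing.

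**Missing dates should be rare.** Step 2 has an ISR evaluation one week after each injection, laboratory abnormalities come from specimens taken at visits, and Protocol 6.4 has incoming safety data checked for completeness and queried. No document shows a missing AE date. A reader might infer that the primary safety result is biased or that events vanish from safety reporting. Neither follows: the number of missing dates may be nil, and an affected event still counts in 12.2 item 2.

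**Average shares would mislead.** For partial dates an average over start dates hides a range as wide as 0% to 100%. Only the 100% for fully missing dates is independent of the start date.

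**Conclusion.** The point holds as a gap in specification. On the natural oral reading and with onset-date assignment, the rule puts every fully undated injection-phase event of an injected participant outside 8.1 and 12.3 and into 12.2 item 1, and dates ISRs before their injection. For partial dates the misplaced share is 0% to 100% (year only) or 0% to about 12% (day missing). The effect on the primary proportion is nil if no date is missing, and at least 11.1 points for each participant whose only qualifying event is misplaced. Whether that has happened cannot be told from these documents, and a dataset specification outside them may define the anchor.

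The BMI table and the CES-D-10 cut-off are wrong as written but affect only baseline description. The clinical study report omits z-scores, and the cut-off conflict affects only a score of exactly 10. Neither adds weight to the main point.

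**What to change.** 1. Define the first dose in Appendix C as the first oral CAB dose, and state in 8.1, 12.2 and 12.3 that events are assigned by onset date.
2. Date an undated ISR to its linked injection, or to the earliest later date that its known parts allow. Keep an ISR linked to a Step 3 injection out of 8.1, because the +8 week visit falls on that window's closing day.
3. For other AEs of injected participants with a missing or partial start date, first assign a phase (oral, injection, or after the 8.1 window) from the known date parts, the stop date or the visit of first report. If the phase cannot be determined, use the injection phase. Then apply the existing rules, but do not let the imputed date fall before that phase begins. An event assigned to the injection phase is not counted in 12.2 item 1, since both windows touch Week 5. For participants never injected, all AEs stay in the oral phase with the oral anchor.
4. Flag every imputed start date and report 8.1 with and without those events.
5. Separately, use the boys' BMI-for-age table in Appendix B, and one CES-D-10 cut-off (10 or more, as in Appendix B) in both places.

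The cost is a few SAP lines and little code. The downside is some over-counting in 8.1 and 12.3 of AEs whose phase cannot be determined. The main case is an undated AE first reported at the first Step 3 visit with a medical history: +12 (Week 45) or +16 (Week 49) in Protocol Appendices III and IV, after a last Step 2 history at Week 34. If onsets were evenly spread, 4/11 = 36% or 8/15 = 53% of that interval lies after Week 41. The flag and the paired report make this visible.
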